We propose to combine regorafenib and PD1 (pembrolizumab) in colorectal cancer patients in 3rd and 4th line setting. Using a phase I/II design, we will first enroll 3-18 patient on phase I to find the recommended dose for phase II. We will then accrue patients to the phase II portion of the trial with the primary efficacy endpoint of PFS. An extensive biomarker analysis, liquid biopsies and tumor tissue, is planned to identify the population who would most benefit from this combination.

Four patients on dose level 1: 80mg were reviewed by the Phase I DLT Committee. One patient was deemed inevaluable for DLT and was replaced. Three patients were evaluable with no DLT. The trial was recommended to proceed to accrue three patients to dose level 2: 120mg. All three patients at this dose level had either grade 2 or grade 3 rash which required a dose reduction at either cycle 2 or 3. It was determined that the dose level 2: 120mg would

be challenging due to its overall tolerability; therefore, dose level 1: 80mg was recommended to expand and enroll additional three patients for a total of 6 patients to be reviewed.

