6.1 Treatments to be administered

Drug	Dose/Potency	Dose Frequency	Route of Administration
Pembrolizumab	200mg	Q3weeks	IV
Regorafenib	Per dose schedule (phase I) RD (Phase II)	Daily days 1-14 of 21 day cycles	PO

Regorafenib starting dose, dose level 1	80mg	Days 1-14
Regorafenib dose level 2	120mg	Days 1-14

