 - Grade 3 dermatologic toxicity (HFSR and non-life threatening events) for ≥ 7 consecutive days;
 - Grade 4 dermatologic toxicity of any duration;
 - \geq Grade 3 immune-related adverse events lasting for ≥ 8 consecutive days despite steroid therapy.

• Combination therapy:

When 70% of the planned regorafenib dose cannot be administered because of toxicity other than DLT during the DLT evaluation period it will be considered DLT. This criteria is in place to ensure the combination can be delivered safely.

Maximum Tolerated Dose (MTD)

During the Phase I portion, the maximum tolerated dose (MTD) is defined as the highest dose tested in which none or only one patient experienced DLT, when at least 6 patients were treated at that dose and are evaluable for toxicity. The MTD is one dose level below the lowest dose tested in which 2 or more patients experienced DLT, unless dose level 3 is established as the MTD. At least 6 patients will be treated at the MTD.

Numbers of Patients and Rules for Dose Escalation

Rules for dose escalation and expansion in cohorts of patients are based on DLT occurring in each patient's first cycle of treatment (21 days without delay or interruption). The standard 3+3 rules will be used. Three patients will be treated at each new dose level. If 0/3 patients experience DLT, 3 patients will be treated at the next dose level. If DLT is experienced in exactly 1/3 patients, 3 more patients (for a total of 6) will be treated at that dose level. If no additional DLT is observed at the expanded dose level (i.e. 1/6 with DLT), the dose will be escalated. Escalation will terminate as soon as two or more patients experience any DLT at a given dose level. The Phase I trial will be closed when 6 patients have been treated at the next lower

dose level, and at most 1/6 patients experience DLT. If more than 1/6 patients experience DLT, the next lower dose will be expanded.

All patients who have not experienced any DLT must be observed for a minimum of 3 weeks after the start of the first cycle, before the dose level is escalated.

There will be no dose escalation within a patient.

Toxicities of interest for Pembrolizumab

- Pneumonitis
- Hepatitis
- Colitis
- Hypothyroidism
- Hypophysitis

Miscellaneous

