6.3.1 Dose Modification Levels

The starting dose of regorafenib is the RD. Study medication will be administered on a 2 weeks on/1 week off schedule [2 weeks out of every 3].

Doses will be delayed or reduced for clinically significant hematologic and non-hematologic toxicities that are related to protocol therapy according to the guidelines shown in the Dose Delays/Dose Modifications table that follows. Dose modifications will follow predefined dose levels. Dose adjustments for hematologic toxicity are based on the blood counts obtained in preparation for the day of treatment.

The modifications of regorafenib will follow the following predefined dose levels:		
Dose level 2	120 mg po qd	Three 40-mg tablets of regorafenib
Dose level 1	80 mg po qd	Two 40-mg tablets of regorafenib

q.d. = *quaque die* (once daily); *q.o.d.* = *quaque altere die* (every other day)

If a subject experiences more than one toxicity, dose reduction should be according to the toxicity with the highest grade

In the case of two or more toxicities of the same grade, the investigator may dose reduce according to that deemed most causally related to study treatment. For Grade 3 toxicity it is acceptable to re-challenge with same dose level at discretion of investigator if toxicity resolved to baseline or lesser grade with medical management within 7 days.

For second occurrence of the same Grade 3 toxicity dose can be reduced to 80mg q.o.d or permanently discontinue at discretion of treating investigator and the rest of the study treatment may be continued. If a dose reduction has been performed, intra-subject dose re-escalation can be considered at the discretion of the treating physician provided that the toxicity(ies) has resolved to baseline.

Tables 6-1, 6-3, and 6-4 outline dose adjustments for toxicities related to regorafenib. Dose adjustment for liver function abnormalities is discussed in table 6-5.

Table 6-1: Recommended dose modification for toxicities except hand-foot-skin reaction, hypertension and ALT/AST/bilirubin			
NCI-CTCAE v5.0^a	Dose Interruption	Dose Modification^b	Dose for Subsequent Cycles
Grade 0-2	Treat on time	No change	No change
Grade 3	Delay until \leq Grade 2 ^c	Reduce by 1 dose level	If toxicity remains < Grade 2, dose re-escalation can be considered at the discretion of the treating investigator. If dose is re-escalated and toxicity (\geq Grade 3) recurs, institute permanent dose reduction.

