10.1 Study design/sample size calculation

A standard 3+3 dose escalation rule will be used during the phase I portion of the study to determine MTD/RP2D of combination of regorafenib and pembrolizumab. 3 dose levels of regorafenib will be assessed. The dose level of pembrolizumab will be fixed. The definitions of DLTs, MTDs, and DLT observation period as well as rules for dose escalation, expansion, and de-escalation are clearly defined in section 6. The study could be stopped when ≥ 2 out of the first 3 patients treated at starting dose experienced DLTs. Or all dose levels are expanded with additional 3 patients. Thus 3 to 18 patients could be enrolled and treated during phase I part of the study.

As soon as MTD/RP2D is determined, the phase II portion of the study will start. We use SWOG's one arm non-parametric survival design to determine the sample size. Progression-free survival will be the primary endpoint. PFS is defined from the start of treatment (day 1 of cycle 1) to the first observation of disease progression or death whichever comes first. The patients are alive and disease progression is not observed, PFS is censored at the date of the latest disease assessment. 63 patients are planned to enroll to have 80% power to detect improvement of median PFS from 1.9 months (CORRECT trial, the historical control, the null hypothesis) to 2.85 months (the alternative hypothesis). The type I error rate using this design will be 0.1 (one sided). The planned accrual time is 2 years and the additional follow-

up time from the end of accrual is 6 months. An expected 20 events are expected to occur during the follow up period.

The approximate upper critical PFS value is 2.44 months.

The total sample size of this phase I/II study is between 3 and 75 patients. Six patients who are treated at MTD/RP2D of the phase I portion of the study will be counted for the phase II portion of the study too.

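### The phase I rules refer to dose levels that the dose tables do not contain and, separately, give no executable step if two or more of six patients at the lowest level have a DLT

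*Combined protocol and SAP*

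**What the plan says.** **Dose levels.** The table in section 6.1 has two regorafenib rows: "Regorafenib starting dose, dose level 1" (80 mg) and "Regorafenib dose level 2" (120 mg). Section 6.3.1 repeats the same two levels under "The modifications of regorafenib will follow the following predefined dose levels". Dosing at 80 mg every other day appears there only as a reduction within a patient, not as a phase I level.

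**MTD and expansion rules (section 6.2).** The first MTD sentence takes the highest dose with at most one DLT among at least six evaluable patients. The second places the MTD one level below the lowest dose with two or more DLTs, "unless dose level 3 is established as the MTD". Two or more DLTs at a level end escalation. Phase I closes once six patients have been treated at the next lower level with at most one DLT. Otherwise: "If more than 1/6 patients experience DLT, the next lower dose will be expanded".

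**Statistics section (10.1).** "3 dose levels of regorafenib will be assessed", with 3 to 18 patients in phase I and 3 to 75 overall. The lower end rests on the study possibly stopping when at least two "out of the first 3 patients treated at starting dose experienced DLTs". For escalation, expansion and de-escalation the section refers back to section 6.

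**State of the trial (section 1.1).** Three evaluable patients at level 1 had no DLT. All three patients at level 2 had grade 2 or 3 rash that led to dose reduction in cycle 2 or 3. Then "dose level 1: 80mg was recommended to expand and enroll additional three patients for a total of 6 patients to be reviewed".

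**The concern.** A 3+3 design is a decision rule, so every result it can produce should map to a step that can be taken. There are two separate mismatches.

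- The text of 6.2 and 10.1 assumes three levels, while both dose tables give two. The stated phase I maximum follows from the wrong count.
- The lowest level has no rule of its own for two or more DLTs among six patients. That cohort is the one section 1.1 describes as next to be reviewed.

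Phase II begins once the MTD/RP2D is determined, and six patients at that dose also count toward phase II. If the adverse result occurred, the next step would have to be decided after the data were seen.

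**Working it through.** **1. The plan's own maxima.** A 3+3 design uses at most six evaluable patients per level. The phase II size in section 10.1 is 63, and six patients are shared between the phases.

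- Three levels: phase I = 3 × 6 = 18; total = 18 + 63 − 6 = 75. Both stated figures reproduce.
- Two levels: phase I = 2 × 6 = 12; total = 12 + 63 − 6 = 69. Neither reproduces.

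These counts are of evaluable patients. Replacements come on top under either scheme; section 1.1 already reports one at level 1.

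**2. The rules applied to level 1.** Inputs: 0/3 DLTs in the first three evaluable patients, three more to come, and three patients at level 2 with no DLT reported. The possible totals at level 1 are therefore 0 to 3 of 6.

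| Rule | 0 or 1 of 6 | 2 or 3 of 6 |
|---|---|---|
| First MTD sentence | Level 1 (level 2 has only three patients) | No dose qualifies |
| Second MTD sentence | Silent: no level with two or more reported DLTs | Points below level 1; no such level |
| Expand the next lower dose | Not called for | No such level |
| Closing condition | Met at level 1 once level 2 is abandoned | Cannot be met |
| Section 10.1 stop (first three patients) | Not triggered | Cannot be triggered: 0/3 already observed |

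The right-hand column is the gap. It does not depend on the level 3 wording: a third level above level 2 would leave it unchanged. Nor does it depend on level 2. Even with two or more DLTs there, level 1 would still be the lowest dose with two or more.

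**3. Chance of reaching the gap.** Given 0/3 so far, it needs at least two DLTs among the three added patients. With true DLT rate p, P = 3p²(1 − p) + p³.

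- p = 0.10: 0.027 + 0.001 = 0.028
- p = 0.20: 0.096 + 0.008 = 0.104
- p = 0.30: 0.189 + 0.027 = 0.216
- p = 0.33: 0.219 + 0.036 = 0.255

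The documents give no DLT rate, so these values of p are assumptions.

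**The case against.** **The adverse outcome is not without consequence.** This stands in part. Escalation terminates under 6.2, no dose meets the first MTD sentence, and phase II cannot open without an MTD/RP2D. Section 12 allows termination for safety findings. Weekly safety meetings, a Phase I DLT Committee and ad hoc DSMC advice are available. It would be wrong to say that nothing follows. None of these, however, says what happens after two or more DLTs among six at level 1, and the instruction that is written cannot be carried out.

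**The stop in section 10.1 only explains the smallest enrolment.** This is fair. It is worded as a possibility and leads into the range of 3 to 18, so it is weak evidence that stopping was meant for the first three patients only. But no other stopping statement is specific to the starting level.

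**The total of 75 could arise with two levels.** The Synopsis gives 69 rather than 63 patients for phase II, and 12 + 69 − 6 = 75. The total alone therefore does not prove a three-level origin. The figure of 18 and the explicit statement of three levels do not have this escape.

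**Do the two MTD sentences conflict at 0 or 1 of 6?** A reader might infer so. They do not: the first gives level 1, and the second applies only where a dose has two or more DLTs, so it is silent.

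**Would naming level 1 as MTD be a wrong conclusion, since no DLT is reported at level 2?** That is also tempting, but the documents do not support it. Level 1 would satisfy the first MTD sentence, level 2 never had the required six patients, and section 1.1 gives no DLT count for level 2. Section 6.2 counts grade 3 skin toxicity lasting at least seven days in cycle 1 as a DLT. The reported rash and later reductions neither establish nor exclude one.

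**The review may already be finished.** Possibly. Section 1.1 speaks of six patients still to be reviewed, yet a footnote to Table 6.3 gives 80 mg as the maximum daily dose, and 6.3.1 takes the RD as the starting dose. The documents do not settle whether the adverse outcome is still open.

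**Conclusion.** The point holds as an inconsistency in a stated rule and its stated sizes, and ranks between a minor correction and one that should be made.

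- The level 3 exception, the three-level statement and the phase I maximum of 18 do not fit the two levels in 6.1 and 6.3.1. On section 10.1's own inputs the maxima fall from 18 to 12 and from 75 to 69.
- Two or more DLTs among six at level 1 lead to an expansion and an MTD at a level that does not exist. The chance is about 3% to 25% for assumed DLT rates of 10% to 33%, taking the three added patients as independent with a common rate and the 0/3 in section 1.1 as final.

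The favourable outcome, 0 or 1 of 6, is covered by the first MTD sentence. If the six-patient review is complete and was favourable, the second item has no further practical effect, but the text would still need correcting.

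**What to change.** Amend sections 6.2 and 10.1 and reconcile them with 1.1, 6.1 and 6.3.1:

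1. State one number of regorafenib dose levels throughout, and remove or correct the reference to dose level 3.
2. Restate the phase I and total maxima to match. If two levels are confirmed and phase II stays at 63, these are 12 and 69 evaluable patients, before replacements. Settle the Synopsis figure of 69 for phase II at the same time.
3. Give one stated outcome for two or more DLTs among six patients at the starting level, worded identically in 6.2 and 10.1.
4. Say in 1.1 whether the six-patient review at level 1 is pending or complete.

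Which dose or clinical action applies is for the sponsor. The cost is a short text amendment, with no added patients or data.

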6.2.1 Regorafenib

Regorafenib tablets will be packaged in high density polyethylene bottles with a white child resistant closure and induction seal. Each bottle includes 30 tablets (for randomized studies) or 28 tablets (for open-label studies) and a 3-gram desiccant. The bottles will have a label affixed containing study identification, product identification, and quantity of tablets. Once the drug has been received it must be kept in a secure, dry location. Study drug must be stored in its original bottle at a temperature not above 25°C (77°F).

The study drug must be exclusively used for the investigation specified in this protocol and it will only be accessible to authorized staff.

6.2.2 Pembrolizumab

Pembrolizumab is provided as a white to off white lyophilized powder (50 mg/vial) or as a liquid solution (100 mg/vial) in Type I glass vials intended for single use only.

Pembrolizumab powder for Solution for Infusion, 50 mg/vial, is reconstituted with sterile water for injection prior to use. Pembrolizumab is formulated with L-histidine as buffering agent, polysorbate 80 as surfactant, sucrose as stabilizer/tonicity modifier, and hydrochloric acid (HCl) and/or sodium hydroxide (NaOH) for pH adjustment (if necessary). The drug

product is stored as a stable lyophilized powder or liquid solution under refrigerated conditions (2°C - 8°C).

The product after reconstitution with sterile water for injection and the liquid drug product is a clear to opalescent solution which may contain extraneous and proteinaceous particulates. The reconstituted product and liquid product is intended for IV administration. The reconstituted drug product solution and liquid drug product can be further diluted with normal saline in IV containers made of polyvinyl chloride (PVC) or non-PVC material. Reconstituted vials should be immediately used to prepare the infusion solution in the IV bag and the infusion solution should be immediately administered. If not used immediately, vials and/or IV bags may be stored at 2-8 °C for up to a cumulative time of 20 hours. If refrigerated, the vials and/or IV bags should be allowed to equilibrate to room temperature prior to subsequent use. Pembrolizumab solutions may be stored at room temperature for a cumulative time of up to 4 hours. This includes room temperature storage of reconstituted drug product solution and liquid drug product in vials, room temperature storage of infusion solution in the IV bag and the duration of infusion.

For each individual trial, clinical supplies are to be stored in accordance with specific instructions on the label.

Information on dosage and administration for any particular study appears in the protocol for that study, including information on compatibility of pembrolizumab and IV infusion bags and components, and the investigator should refer to the protocol for exact details.

Important Safety Considerations

Pembrolizumab is a humanized monoclonal Ab. Thus far, no serious infusion reactions have been reported however, patients should be closely monitored for potential AEs during antibody infusion and potential AEs throughout the study. In the event that a subject experiences an allergic reaction to pembrolizumab, treatment (i.e., vasopressors, H2-blockers, antihistamines, H1-blockers, steroids) should be administered, as appropriate, and prophylaxis should be considered (please see the IB).³²

6.3 Study Treatment

Please see details on section 6.1.

Regorafenib tablets should be taken once a day with approximately 8 fluid ounces (240 mL) of water after a low-fat (<30%) fat meal. Some examples of low fat meals are:

- Two slices of white toast with 1 tablespoon of low-fat margarine and 1 tablespoon of jelly and 8 ounces (240 mL) of skim milk (approximately 319 calories and 8.2 g of fat).
- One cup of cereal (i.e. Special K), 8 ounces (240 mL) of skim milk, one piece of toast with jam (no butter or marmalade), apple juice, and one cup of coffee or tea (2 g fat, 17 g protein, 93 g of carbohydrate, 520 calories).

6.3.1 Dose Modification Levels

The starting dose of regorafenib is the RD. Study medication will be administered on a 2 weeks on/1 week off schedule [2 weeks out of every 3].

Doses will be delayed or reduced for clinically significant hematologic and non-hematologic toxicities that are related to protocol therapy according to the guidelines shown in the Dose Delays/Dose Modifications table that follows. Dose modifications will follow predefined dose levels. Dose adjustments for hematologic toxicity are based on the blood counts obtained in preparation for the day of treatment.

The modifications of regorafenib will follow the following predefined dose levels:		
Dose level 2	120 mg po qd	Three 40-mg tablets of regorafenib
Dose level 1	80 mg po qd	Two 40-mg tablets of regorafenib

q.d. = *quaque die* (once daily); *q.o.d.* = *quaque altere die* (every other day)

If a subject experiences more than one toxicity, dose reduction should be according to the toxicity with the highest grade

In the case of two or more toxicities of the same grade, the investigator may dose reduce according to that deemed most causally related to study treatment. For Grade 3 toxicity it is acceptable to re-challenge with same dose level at discretion of investigator if toxicity resolved to baseline or lesser grade with medical management within 7 days.

For second occurrence of the same Grade 3 toxicity dose can be reduced to 80mg q.o.d or permanently discontinue at discretion of treating investigator and the rest of the study treatment may be continued. If a dose reduction has been performed, intra-subject dose re-escalation can be considered at the discretion of the treating physician provided that the toxicity(ies) has resolved to baseline.

Tables 6-1, 6-3, and 6-4 outline dose adjustments for toxicities related to regorafenib. Dose adjustment for liver function abnormalities is discussed in table 6-5.

Table 6-1: Recommended dose modification for toxicities except hand-foot-skin reaction, hypertension and ALT/AST/bilirubin			
NCI-CTCAE v5.0^a	Dose Interruption	Dose Modification^b	Dose for Subsequent Cycles
Grade 0-2	Treat on time	No change	No change
Grade 3	Delay until \leq Grade 2 ^c	Reduce by 1 dose level	If toxicity remains < Grade 2, dose re-escalation can be considered at the discretion of the treating investigator. If dose is re-escalated and toxicity (\geq Grade 3) recurs, institute permanent dose reduction.
Grade 4	Delay until \leq Grade 2 ^c	Reduce by 1 dose level. Permanent discontinuation can be considered at treating investigator's discretion.	

a. NCI-CTCAE = National Cancer Institute - Common Terminology Criteria for Adverse Events, version 5.0
 
b. Excludes alopecia, non-refractory nausea/vomiting, non-refractory hypersensitivity and nonclinical and asymptomatic laboratory abnormalities.
 
c. If no recovery after a 4 week delay*, treatment should be permanently discontinued unless subject is deriving clinical benefit.
			

The table above outlines dose adjustments for hematologic and non-hematologic toxicities related to regorafenib except HFSR and hypertension.

In addition to these recommended dose modifications, subjects who develop diarrhea, mucositis, anorexia or other events predisposing to fluid loss or inadequate fluid intake should be carefully monitored and rehydrated as clinically necessary. This is in order to minimize the risk of postural hypotension and renal failure.

Table 6-2: Grading for Hand-Foot-Skin-Reaction

	Grade 1	Grade 2	Grade 3
NCI-CTCAE v5.0 Palmar-plantar erythrodysesthesia syndrome	Minimal skin changes or dermatitis (e.g., erythema, edema, or hyperkeratosis) without pain	Skin changes (e.g., peeling, blisters bleeding, edema, or hyperkeratosis) with pain	Severe skin changes (e.g., peeling, blisters, bleeding, edema, or hyperkeratosis) with pain
Further description / examples of skin changes	Numbness, dysesthesia / paresthesia tingling, painless swelling, or erythema of the hands and/or feet	Painful erythema and swelling of the hands and/or feet	Moist desquamation, ulceration, blistering, or severe pain of the hands and/or feet
Effect on activities	Does not disrupt normal activities	Limiting instrumental activities of daily life (e.g., preparing meals, shopping for groceries or clothes, using the telephone, managing money)	Limiting self-care activities of daily life (e.g., bathing, dressing and undressing, feeding self, using the toilet, taking medications) and not bedridden
a. Palmer-planter erythrodysesthesia syndrome is a disorder characterized by redness, marked discomfort, swelling, and tingling in the palms of hands or the soles of the feet.			

Table 6.3 Recommended dose modification for hand-foot-skin reaction (HFSR)		
Grade of event (NCI-CTCAE v5.0)	Occurrence	Suggested Dose Modification
Grade 1	Any	Maintain dose level and immediately institute supportive measures for symptomatic relief
Grade 2	1 st occurrence	Consider decreasing dose by one dose level and immediately institute supportive measures. If no improvement, interrupt therapy for a minimum of 7 days, until toxicity resolves to Grade 0-1 ^{b, c}
	No improvement within 7 days or 2 nd occurrence	Interrupt therapy until toxicity resolves to Grade 0-1. ^c When resuming treatment, treat at reduced dose level ^b If dose reduced from the 1 st occurrence then discontinue therapy.
	3 rd occurrence	Discontinue therapy
	4 th occurrence	Discontinue therapy
Grade 3	1 st occurrence	Institute supportive measures immediately. Interrupt therapy for a minimum of 7 days until toxicity resolves to Grade 0-1. ^c When resuming treatment, decrease dose by one dose level. ^{b, d}
	2 nd occurrence	Discontinue therapy
	3 rd occurrence	Discontinue treatment permanently.

a. More conservative management is allowed if judged medically appropriate by the investigator.
 
b. If toxicity returns to Grade 0-1 after dose reduction, dose re-escalation is permitted at the discretion of the investigator if subject has completed one cycle at reduced dose without recurrence of event.
 
c. If there is no recovery after a 4-week delay, treatment with regorafenib will be discontinued permanently.
 
d. Subjects requiring > 1 dose reductions should go off protocol therapy.
 
e. The maximum daily dose is 80 mg. If reduction required resulting in a dose of less than 80mg qod of regorafenib, then regorafenib will be permanently discontinued.
		

Specific guidance for skin and subcutaneous disorders other than HFSR (includes rash, rash erythematous, rash follicular, rash generalized, rash macular, rash maculopapular, rash papular, rash pruritic, exfoliative rash, pruritus, eczema, dermatitis)		
Event	Regorafenib	Pembrolizumab
G2	
 No modifications 	
 Consider withholding for persistent symptoms Restart at same dose if resolution to ≤ G1 or baseline ≤ 12 weeks of last infusion Consider discontinuation if NO resolution ≤ 12 weeks of last infusion ¹

G3	
 • Hold until recovery to \leq G2 and restart at same dose level or reduce 1 dose level ^a (at the investigator's discretion) • 1st + 2nd re-appearance: Hold until recovery to \leq G2 and reduce 1 dose level ^a (at the investigator's discretion) • 3rd re-appearance: Discontinue 	
 • Hold and restart at same dose if resolution to \leq G1 or baseline \leq 12 weeks of last infusion • Hold and discontinue if NO resolution \leq 12 weeks of last infusion ^b
G4 (when applicable)	
 • Hold until recovery to \leq G2 and reduce 1 dose level ^a • 1st re-appearance: Discontinue 	
 • Discontinue ^b

¹ If toxicity returns to Grade 0-1 after dose reduction, dose re-escalation is permitted at the discretion of the investigator if subject has completed one cycle at reduced dose without recurrence of event.

a: If reductions are required resulting in a dose of less than 80 mg q.o.d. of regorafenib, then regorafenib will be permanently discontinued. For grade 3, patient could stay on regorafenib for the first appearance, or hold until resolved to grade 2 or less, restart at the same dose level or lower after discussion between investigator and study chair.

b: after consultation with study chair, if toxicity considered at least possibly related to pembrolizumab.

If reduction required resulting in a dose of less than 80mg qod of regorafenib, then regorafenib will be permanently discontinued.

(For studies with combination therapy, consider including the following statement "The other study treatment may be continued").

At first occurrence of HFSR, independent of grade, prompt institution of supportive measures such as topical emollients, low potency steroids, or urea-containing creams should be administered.

Recommended prevention/management strategies for skin toxicities consistent with HFSR are summarized below:

Control of calluses

Before initiating treatment with regorafenib:

- Check condition of hands and feet.
- Suggest a manicure/pedicure, when indicated.
- Recommend pumice stone use for callus or 'rough spot' removal.

During regorafenib treatment:

- Avoid pressure points.
- Avoid items that rub, pinch or create friction.

Use of creams

- Non-urea based creams may be applied liberally.

- Keratolytic creams (e.g. urea-based creams, salicylic acid 6%) may be used sparingly and only to affected (hyperkeratotic) areas.
- Alpha hydroxyl acids (AHA) based creams may be applied liberally 2 times a day. Approximately 5% to 8% provides gentle chemical exfoliation.
- Topical analgesics (e.g. lidocaine 2%) are to be considered for pain control.
- Topical corticosteroids like clobetasol 0.05% should be considered for subjects with Grade 2 or 3 HFSR. Avoid systemic steroids.

Tender areas should be protected as follows:

- Use socks/gloves to cover moisturizing creams
- Wear well-padded footwear
- Use insole cushions or inserts (e.g. silicon, gel)
- Foot soaks with tepid water and Epson salts

Hypertension

Hypertension is a known AE associated with regorafenib treatment. Subject will have their blood pressure measured at least weekly at the study site during the first 6 weeks of treatment. If additional blood pressure measurements are done outside the study site, and the blood pressure is > 140 mm Hg systolic or > 90 mm Hg diastolic (NCI CTCAE v5.0), then the subject must contact study personnel. The management of hypertension, including the choice of antihypertensive medication, will be performed according to local standards and to the usual practice of the investigator. Every effort should be made to control blood pressure by medical means other than study drug dose modification. If necessary, Table 6-4 outlines suggested dose reductions.

Table 6-4: Management of Treatment-Emergent Hypertension

Grade (CTCAE v5.0)	Antihypertensive Therapy	Regorafenib Dosing
1 Prehypertension (systolic BP 120 - 139 mmHg or diastolic BP 80 - 89 mmHg)	None	
 Continue regorafenib Consider increasing blood pressure (BP) monitoring
2 Systolic BP 140 - 159 mmHg or diastolic BP 90 - 99 mmHg, OR Symptomatic increase by > 20 mmHg (diastolic) if previously within normal limits	Treat with the aim to achieve diastolic BP ≤ 90 mm Hg: If BP previously within normal limits, start anti-hypertensive monotherapy If patient already on anti-hypertensive medication, titrate up the dose.	
 Continue regorafenib If symptomatic, hold regorafenib until symptoms resolve AND diastolic BP ≤ 90 mm Hg^a. When regorafenib is restarted, continue at the same dose level.
3 Systolic BP ≥ 160 mmHg or diastolic BP ≥ 100 mmHg OR More than one drug or more intensive therapy than previously used indicated	Treat with the aim to achieve diastolic BP ≤ 90 mm Hg: Start anti-hypertensive medication AND/OR Increase current anti-hypertensive medication AND/OR Add additional anti-hypertensive medications.	
 Hold regorafenib until diastolic BP ≤ 90 mm Hg, and if symptomatic, until symptoms resolve.^a When regorafenib is restarted, continue at the same dose level. If BP is not controlled with the addition of new or more intensive therapy, reduce by 1 dose level.^b If Grade 3 hypertension recurs despite dose reduction and antihypertensive therapy, discontinue therapy
4 Life-threatening consequences (eg, malignant hypertension, transient or permanent neurologic deficit, hypertensive crisis)	Per institutional guidelines	Discontinue therapy

a. Patients requiring a delay of >4 weeks should go off protocol therapy
 
b. If BP remains controlled for at least one cycle, dose re-escalation permitted per investigator's discretion.
 
c. Patients requiring >1 dose reductions should go off protocol therapy. If reduction required resulting in a dose of less than 80mg q.o.d of regorafenib, then regorafenib will be permanently discontinued.
		

Liver Function Abnormalities

For patients with observed worsening of serum liver tests considered related to regorafenib (i.e. where no alternative cause is evident, such as post-hepatic cholestasis or disease progression), the dose modification and monitoring advice in Table 6-5 should be followed.

Regorafenib is a UGT1A1 inhibitor. Mild, indirect (unconjugated) hyperbilirubinemia may occur in patients with Gilbert's syndrome.

Table 6.5: Dose Modification/interruption for LIVER toxicity

General instructions:

If any of below outlined events will occur: Monitor liver function tests weekly or more frequently until recovery to baseline or stabilization.

If reduction required resulting in a dose of less than 80mg qod of regorafenib, then regorafenib will be permanently discontinued.

For any G3/4 increases in ALT/AST or bilirubin:

If the increases are primarily seen under ongoing regorafenib treatment (e.g. last pembrolizumab infusion was given one week before):

Closely monitor for potential de-challenge, i.e. whether a decrease in ALT/AST and/or bilirubin values is seen within 3 days of regorafenib interruption.

In case no such decrease is seen and/or a further deterioration in liver function is seen: Administer corticosteroids (initial dose of 1-2 mg/kg prednisone or equivalent) followed by taper

If immune-related hepatitis is suspected: Directly follow guidance provided in Table 6-6

EVENT	Regorafenib	Pembrolizumab
If ALT/AST $\leq 2 \times$ ULN at baseline AND $> 5 \times$ ULN OR ALT/AST $> 2 \times$ ULN at baseline and 3 fold increase from Baseline BUT NOT EXCEEDING $8 \times$ ULN	Assess according to guidance given in Table 6-6 
 Hold until recovery to \leq G2 or baseline, then reduce 1 dose level 1st re-appearance: discontinue 	Hold and assess + decide on potential restart according to guidance given in Table 6-6
ALT or AST $> 5 \times$ ULN accompanied by a hyperbilirubinemia $\geq 2 \times$ ULN or $>50\%$ increase from total bilirubin level from baseline	Discontinue and assess according to guidance given in Table 6-6 A patient with Gilbert's syndrome should be managed according to observed elevation of ALT and/or AST if the observed bilirubin increase is below actual increased baseline bilirubin value	Hold and assess + decide on potential restart according to guidance given in Table 6-6
t-bilirubin >2 mg/dL and ALT/AST $\leq 5 \times$ ULN	No modifications	Hold and assess + decide on potential restart according to guidance given in Table 6-6
Any t-bilirubin > 3.0 mg/dL irrespective of ALT/AST values	Assess according to guidance given in Table 6-6	Hold and assess + decide on potential restart according to guidance given in Table 6-6

	
 Hold until recovery to \leq G1 or baseline, then reduce 1 dose level 1st re-appearance: Discontinue 	
AST and / or ALT > 20 x ULN	Discontinue and assess according to guidance given in Table 6-6	Discontinue and assess according to guidance given in Table 6-6

Table 6.6: Guidance on assessment and further dosing following occurrence of hepatic events of clinical interest

Assessment procedure to be applied

- Notification of Bayer and Merck within 24 hours via SAE report
- Obtain a work-up for hepatitis, including hepatitis A, B, C, D, E, EBV (Epstein-Barr virus), CMV (cytomegalovirus)
- Assess for ingestion of drugs/supplements with hepatotoxic potential and alcohol ingestion
- Assess for potential bacterial infection, biliary obstruction, or occult gastrointestinal bleeding
- Other laboratories or imaging studies as clinically indicated
- Consider liver biopsy
- Infection needs to be ruled out with cultures of blood, urine, and ascites (if possible), as well as
- chest X-ray and abdominal imaging if relevant. If an infection is found, antibiotics should be
- started
- If biliary obstruction is present, consultation with a gastroenterologist and/or an interventional
- radiologist should be obtained to see if the obstruction may be relieved
- A careful review of drugs, including herbal and alternative medications should be obtained

Immune-related hepatitis due to study treatment should be suspected if any of the following is seen (Immune-related hepatitis is a diagnosis made after excluding other possible etiologies for the change. Viral flare (if applicable), biliary or vascular obstruction, infection, medications, and alcohol use must be ruled out):

- AST or ALT baseline values are less than $2 \times$ ULN, and AST or ALT laboratory values increase to $\geq 5 \times$ ULN
- Among patients with baseline ALT or AST $\geq 2 \times$ ULN, levels increase to $> 3 \times$ the baseline level
- AST/ALT > 500 U/L regardless of baseline level
- Among patients with baseline Tbil levels < 1.5 mg/dL: a value of > 2.0 mg/dL
- Total bilirubin > 3.0 mg/dL regardless of baseline level management
- Interrupt study treatment and alert Bayer and Merck
- Start i.v. corticosteroid (methylprednisolone 125 mg or equivalent) followed by oral corticosteroid
- Monitor with weekly laboratory tests including AST, ALT, Tbil, Dbil, ALP, and INR.

If symptoms and laboratory tests resolve to Grade ≤ 1 or baseline (if abnormal at baseline), taper steroids over 28 days. Study treatment may be restarted after steroid treatment has been tapered to prednisone ≤ 10 mg/day (or equivalent dose of another agent).

If laboratory abnormalities do not resolve within 3 weeks, or steroids cannot be lowered to ≤ 10 mg/day (or prednisone equivalent) within 12 weeks, or patients show evidence of decompensation treatment must be permanently discontinued.

For toxicity management guidelines for pembrolizumab please refer to appendix 2, section 16.2.

Prevention/management strategies for diarrhea

Diarrhea can be a common side effect of regorafenib. The preventive/management strategies for diarrhea should be consistent with local standards (e.g., anti-diarrheals and optimized hydration status).

